4.1.1 PK sub-study

A PK sub-study in Japanese and non-Japanese patients will be performed following the 12 weeks of treatment. For PK sampling details, refer to [Table 1-2](#).

For the PK sub-study, 30 Japanese and 30 non-Japanese patients will be randomised with ratio 3:1:3:1:3:1:3 as randomised in the main trial (for details on randomisation ratio, refer to [Figure 4-1](#)). For further details on randomisation, see Section [6.3.1](#).

The aim of the PK sub-study is to assess and compare the PK properties of three doses of oral NNC0385-0434 at steady-state between Japanese and non-Japanese patients (18 Japanese and 18 non-Japanese patients exposed to NNC0385-0434). The evolocumab arm is not part of the PK sub-study. Therefore, patients randomised to the evolocumab arm will not have additional visits or sub-study PK samples taken.

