6.3 Measures to minimise bias: Randomisation and blinding

6.3.1 Randomisation

- This is a randomised, placebo-controlled trial.
- Patients will be randomised 3:1:3:1:3:1:3 according to [Figure 4-1](#)
- For the PK sub-study:
 - All Japanese patients will be included in the PK sub-study. Once 30 Japanese patients have been included in the PK sub-study and randomised to treatment, any Japanese patient ongoing screening procedures should be considered a screen failure (Section [5.4](#)).
 - Selected non-Japanese sites will include 30 non-Japanese patients for the PK sub-study. Once 30 non-Japanese patients have been randomised to the PK sub-study, eligible non-Japanese patients will be randomised to the main study.
- Randomisation will be stratified according to participation in the PK sub-study (yes/no), country (Japan/non-Japan) and population (inclusion criteria 3a/3b). Within each stratum, each patient will be randomly allocated to one of the treatment arms.
- All patients will be screened and randomised centrally using IWRs and assigned to the next available treatment according to randomisation schedule. Trial product will be dispensed/allocated at the trial visits summarised in the flowchart ([Table 1-1](#)).
- At screening, each patient will be assigned a unique 6-digit number which will remain the same throughout the trial. Each site is assigned a 3-digit number and all patient numbers will start with the site number.

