9.4.2 Primary endpoint

Definition of primary endpoint: Percent change in LDL-C

Change from randomisation at week 0 to week 12 in LDL-C (%) is defined as:

$$\% \text{ LDL-c change} = \frac{(\text{LDL-C at week 12} - \text{LDL-C at baseline})}{\text{LDL-C at baseline}} \times 100\%$$

The primary estimand for percent change in LDL-C addresses the efficacy of oral NNC0385-0434 and will be estimated based on the FAS using the on-treatment observation period.

The primary analysis for the primary estimand for percent change in LDL-C is an analysis of covariance (ANCOVA) with randomised treatment (each oral NNC0385-0434 dose, pooled placebo group, and s.c. evolocumab) and strata as factors (population strata (inclusion criteria 3a/3b), country (Japan/non-Japan)) and baseline LDL-C as a covariate.

The estimated treatment difference between individual oral NNC0385-0434 doses and placebo will be reported together with the associated two-sided 95% CI and corresponding two-sided p-value.

Handling of missing week 12 values for the primary estimand

The primary estimand will be estimated based on the FAS using post-baseline measurements up to and including week 12 from the on-treatment observation period. Missing data and observations outside the on-treatment observation period such as week 12 assessments for retrieved dropouts will be imputed using multiple imputation assuming missing at random (MAR). Missing post-baseline data will be imputed sequentially within each treatment using the observed post-randomisation assessments for visits prior to the one in question obtained during the on-treatment observation period. The imputation model will include strata as factors (population strata (inclusion criteria 3a/3b), country (Japan/non-Japan)) and baseline and post-baseline LDL-C values prior to the visit in question as covariates. The proportion of missing LDL-C change data at week 12 is assumed to be no more than 10% and is expected to be similar in all treatment arms.

Analysis addressing the effect of oral NNC0385-0434 vs. s.c. evolocumab

This analysis will evaluate the treatment difference between oral NNC0385-0434 and s.c. evolocumab using the same analysis as the primary analysis for the primary estimand described above. However, the treatment differences between oral NNC0385-0434 doses and s.c. evolocumab will be estimated but no confirmatory testing will be carried out.

Analyses addressing the additional estimand

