The analysis model for percent change in LDL-C is an ANCOVA with randomised treatment and strata as factors (population strata (inclusion criteria 3a/b), country (Japan/non-Japan)) and baseline LDL-C as a covariate.

Handling of missing week 12 values for the additional estimand

The additional estimand will be estimated based on the FAS using week 12 measurements from the in-trial observation period. Missing week 12 data will be imputed using multiple imputation assuming missing at random (MAR). Imputation will be done within groups defined by randomised treatment and treatment status at week 12. The imputation model will include strata as factors (population strata (inclusion criteria 3a/3b), country (Japan/non-Japan)) and baseline LDL-C as a covariate. In case of sparse data in some of the groups, a common treatment discontinuation group across treatments will be created and randomised treatment will be added to the model as factor. If this is still not sufficient, the model will be thinned in the following order, starting with the one that will be removed first; strata, randomised treatment, and baseline value.

Dose-response modelling

In order to evaluate the effect of oral NNC0385-0434 dose vs. placebo on percent change in LDL-C and to characterise the dose-response relationship the mean percent LDL-C change will be estimated using dose as a continuous variable.

The dose-response candidate models in [Table 9-2](#) will be fit.

Table 9-2 Dose-response candidate models

Model	Functional form $f(d, \theta)$
E_{max}	$E_0 + E_{max} \frac{d}{ED_{50} + d}$
Linear	$E_0 + \beta d$

The candidate models will be fit to the estimated percent change in LDL-C means at week 12 for the employed oral NNC0385-0434 doses and placebo from the primary analysis model described above. Thus, all patients in the FAS will be included and the same assumptions regarding missing values and the impact of explanatory variables will be applied.

The model used to evaluate dose-response will be selected among the candidate models based on the best fit to data. The best fit will be evaluated based on convergence, model complexity, Akaike information criterion (AIC) value and visual evaluation.

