5.4.2 Supportive secondary endpoints

The following supportive secondary endpoints

- change in total cholesterol
- change in HDL-cholesterol
- change in VLDL-cholesterol
- change in triglycerides
- change in total Apo B
- change in total Apo CIII

are computed similar as the primary endpoint, that is for each of these six lipid/lipoprotein parameters, the percentual change from randomisation at week 0 to week 12 is defined as:

$$\% \text{ parameter change} = \frac{(\text{parameter value at week 12} - \text{parameter value at baseline})}{\text{parameter value at baseline}} \times 100\%$$

Each of these six endpoints will be analysed separately by an analysis of covariance (ANCOVA) with randomised treatment (each oral NNC0385-0434 dose, pooled placebo group, and s.c. evolocumab) and strata as factors (population strata (inclusion criteria 3a/3b), country (Japan/non-Japan)) and baseline parameter value as a covariate.

The parameter Lipoprotein a (Lp(a)) follows a log-normal distribution and will be log-transformed before analysis. The supportive secondary endpoint: Change in total Lp(a) (from baseline (week 0) to visit 9 (week 12)), will be reported as the result of the difference in log-transformed Lp(a) back-transformed to the original scale, implying that log-treatment-differences are reported as treatment ratios. Confidence intervals for the treatment ratios will be calculated as exponential upper and lower limits for log-treatment difference confidence intervals.

Safety endpoints

The secondary endpoint Treatment-emergent adverse events (TEAE) is the number of AEs recorded during the on-treatment period (see [section 4](#) for the definition of the on-treatment period). All AEs will be coded using the most recent version of the Medical Dictionary for Regulatory Activities (MedDRA)

Summaries of TEAEs are presented as an overview including all AEs, serious AEs, AEs leading to withdrawal, AEs by severity, AEs by relation to treatment and outcome of AEs. Furthermore, summary tables based on system organ class and preferred term is made for:

- All TEAEs
- Serious TEAEs
- TEAEs evaluated to be probably or possibly related to the trial products
- TEAEs by severity
- Serious TEAEs evaluated to be probably or possibly related to the trial products

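### PK sub-study participation is a randomisation stratum but is left out of the efficacy ANCOVAs: a small precision point, without bias

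*Protocol*

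**What the plan says.** Protocol 6.3.1 names three stratification factors: "Randomisation will be stratified according to participation in the PK sub-study (yes/no), country (Japan/non-Japan) and population (inclusion criteria 3a/3b"). Protocol 4.1 and the synopsis list the same three.

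The analysis models name two of them. For the primary estimand, Protocol 9.4.2 has "strata as factors (population strata (inclusion criteria 3a/3b), country (Japan/non-Japan)) and baseline LDL-C as a covariate", and SAP 5.3.2 repeats it. For the additional estimand both documents specify an "ANCOVA with randomised treatment and strata as factors (population strata (inclusion criteria 3a/b), country (Japan/non-Japan)) and baseline LDL-C as a covariate". The comparison with evolocumab uses the primary analysis model. For six of the supportive lipid endpoints, SAP 5.4.2 has "strata as factors (population strata (inclusion criteria 3a/3b), country (Japan/non-Japan)) and baseline parameter value as a covariate". The imputation models in Protocol 9.4.2 and SAP 5.3.2 also use population and country only.

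On who is in the sub-study, Protocol 6.3.1 says "All Japanese patients will be included in the PK sub-study" and "Selected non-Japanese sites will include 30 non-Japanese patients for the PK sub-study". The allocation ratio is the same as in the main trial: "30 Japanese and 30 non-Japanese patients will be randomised with ratio 3:1:3:1:3:1:3" (Protocol 4.1.1).

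**The concern.** The protocol and SAP agree with each other. The mismatch is between how patients are randomised and how they are analysed. A reader who sees strata announced as factors and then two of three listed cannot tell whether the third was dropped on purpose.

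Stratifying on a prognostic variable balances it across arms. If the model then ignores that variable, its variance stays in the residual, and the model-based standard error is larger than the true variability of the estimate. The trial is sized on confidence-interval half-width (Protocol 9.2), so precision is what could be lost.

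The route to a loss is narrow. The extra sampling comes after treatment ("A PK sub-study in Japanese and non-Japanese patients will be performed following the 12 weeks of treatment"), and Table 1-2 note e has the visit 9 lipids taken before that visit's dose. For patients who stay on treatment, a difference in week 12 LDL-C change would have to come from who enters the sub-study: selected sites, the parental-descent criterion in Protocol 5.1, and possibly calendar time, because non-Japanese patients go to the main study once the 30 places are filled.

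**Working it through.** **Inputs from the documents.** 255 patients in five analysis groups of 51 (placebo pooled). 30 Japanese patients, all in the sub-study; 30 non-Japanese sub-study patients; 255 − 60 = 195 others. SD 30 points, 45 eligible per group, half-width targets of 14 and 13 points (Protocol 9.2 and Table 9-1).

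**Input not in the documents.** D is the difference in percent LDL-C change between sub-study and other non-Japanese patients that remains after baseline LDL-C, population and country. It is assumed, with 5 and 10 points as the main cases and 20 and 30 as deliberately large ones.

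**Step 1: reproduce the plan's figure.** P(t(0.975, 88) × s × √(2/45) ≤ w), where 88 × s²/SD² is chi-square with 88 df and SD = 30. This gives 93.7% for w = 14 (stated 94%) and 69.2% for w = 13 (stated 69%). The expected half-width is about 1.987 × 30 × √(2/45) = 12.57 points.

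**Step 2: variance left unmodelled.** With country in the model, participation varies only among the 225 non-Japanese patients:

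extra residual variance = (30 × 195/225)/255 × D²/SD² = 0.102 × D²/SD².

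| D (SD 30) | Extra variance | Interval widening | Patients (255 × extra) | P(half-width ≤ 14) | P(half-width ≤ 13) |
|---|---|---|---|---|---|
| 0 | 0 | 0 | 0 | 93.7% | 69.2% |
| 5 | 0.28% | 0.14% | 0.7 | 93.5% | 68.6% |
| 10 | 1.13% | 0.56% | 2.9 | 92.7% | 66.5% |
| 20 | 4.5% | 2.2% | 11.6 | 88.9% | 58.1% |
| 30 | 10.2% | 5.0% | 26.0 | 80.3% | 44.2% |

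Widening is √(1 + extra) − 1. The probabilities use SD = 30 × √(1 + extra), so they take 30 as the SD with the factor included. At SD 34, the upper value in Protocol 9.2, widening is 0.11% and 0.44% for D = 5 and 10.

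**Step 3: cost of the factor.** Residual df go from 255 − 8 = 247 to 246, and the t quantile from 1.96961 to 1.96965.

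**Step 4: simulation with imputation as planned, 100 mg against pooled placebo.** 15,000 trials per D, with participation left out of the within-arm imputation. Assumed: population split 70/30, blocks of 15, residual SD 30, 10% missing at week 12 with half of these also missing at week 9, within-patient correlation 0.7, and 50 imputations rather than the planned 1000. Trials in which an arm had no observed patient in one level of country or population were redrawn.

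| D | Mean half-width, omitted | Mean half-width, included | Paired difference |
|---|---|---|---|
| 0 | 12.401 | 12.407 | −0.006 |
| 5 | 12.423 | 12.415 | +0.008 |
| 10 | 12.466 | 12.416 | +0.050 |

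Coverage was 95.3% to 95.4% throughout. Mean bias was at most 0.09 points (Monte Carlo SE 0.05) and the same to within 0.002 with or without the factor. The benefit before cost is 0.050 + 0.006 = 0.056 points at D = 10, or 0.00056 per unit of D². Break-even is therefore √(0.006/0.00056), about 3 points.

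**Step 5: larger D.** A separate simulation (4,000 trials per D, no imputation, 12% missing) gave half-widths of 12.79 against 12.52 points at D = 20 and 13.15 against 12.52 at D = 30, omitted against included. At D = 30 without the factor, the mean model SE was 6.67 and the empirical SD 6.47, so the interval errs on the wide side.

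**The case against.** The strongest reply is that no harm is shown. There is no bias, the direction is conservative, and the only loss depends on a D the documents do not give. Below about 3 points the extra factor makes intervals wider, by up to 0.006 points. The protocol and SAP agree, neither promises to adjust for every stratum, and the stratum may exist only to secure 18 Japanese and 18 non-Japanese exposed patients in the sub-study. All of this is fair. It fixes the grade at minor, but it does not explain the omission in the plan, and the cost when D is zero is negligible.

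Second, Table 9-1's method uses two groups (88 df), while the planned ANCOVA pools five. With 45 per group, df are 225 − 8 = 217. P(half-width ≤ 14) is then 99.5%, falling to 99.4% and 99.2% at D = 5 and 10. P(half-width ≤ 13) is 82.1%, falling to 81.3% and 78.8%. The loss is smaller at 14 points and similar at 13. This stands as a qualification.

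Third, adding the factor to the ANCOVA but not to the imputation model leaves the two unmatched, and small cells are not a distinguishing reason: about 30 × 3/15 = 6 non-Japanese sub-study patients per arm is also the number of Japanese patients per arm, and country is in the imputation model. That criticism of the reason is right. It does not defeat the change: bias and coverage were unaffected by the split version, and a further small simulation gave almost the same intervals when the factor was in both models.

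**Conclusion.** The point holds and is minor. One of three randomisation strata is missing, without explanation, from every efficacy ANCOVA that lists its strata. Because the allocation ratio is the same inside and outside the sub-study, the omission neither biases the treatment differences nor inflates type I error.

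The possible loss is in interval width only: below 1% for D up to 10 points, and nothing material if D is near zero. It would reach 5% only if sub-study patients differed from other non-Japanese patients by a full SD, and nothing in the documents suggests that. These sizes rest on the assumed D, on the protocol's SD of 30 points, and, for the simulations, on the assumed population split and missing-data pattern.

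**What to change.** Add PK sub-study participation (yes/no) as a factor in the ANCOVAs for the primary estimand, the additional estimand, the evolocumab comparison and the six lipid endpoints whose strata are listed (Protocol 9.4.2; SAP 5.3.2 and 5.4.2). The imputation models and their thinning order can stay as planned: they are fitted in small groups, and leaving the factor out of them did no visible harm.

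The cost is one model term and one residual degree of freedom per ANCOVA. No new data are needed, because participation is already recorded for randomisation. If the sponsor prefers the present model, one sentence in the SAP giving the reason would settle the matter. Either change should be made before unblinding.

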6.3.2 Blinding

- This trial is double-blinded within dose level of oral NNC0385-0434 and size-matched placebo arm. Within dose level, oral NNC0385-0434 and placebo tablets are identical in appearance and will be packed in a manner that maintains blinding.
- The s.c. evolocumab arm is open label and treatment for a patient will be assigned using IWRs.

6.3.3 Blind break

The IWRS will be used for blind-breaking. In case of an emergency, the investigator has the sole responsibility for determining if unblinding of a patient's treatment is warranted. Patient safety must always be the first consideration in making such a determination. If the investigator decides that unblinding is warranted, the investigator should make every effort to contact Novo Nordisk prior to unblinding a patient's treatment unless this could delay emergency treatment of the patient. If a patient's treatment is unblinded, Novo Nordisk (Global Safety department) must be notified within 24 hours after breaking the blind. The date and reason that the blind was broken must be recorded in the source documentation. The person breaking the blind must print the "code break confirmation" notification generated by the IWRS, sign and date the document. If IWRS is not accessible at the time of blind break, the IWRS helpdesk should be contacted. Contact details are listed in [Attachment I](#).

Treatment with trial product can be resumed if there are no safety concerns at the discretion of the investigator.

For the early PK monitoring the laboratory will also have access to the treatment allocation. The laboratory responsible for analysis of NNC0385-0434 (LC-MS/MS analysis) and the responsible bioanalytical scientist at special lab will have access to the treatment allocation. The Novo Nordisk scientific monitor for bioanalysis will have access to treatment allocation according to PK sample but will be blinded to subject level. Also, treatment allocation will be accessible to the laboratory responsible for analysis of anti-drug antibodies and the responsible immunogenicity scientist at Novo Nordisk.

6.4 Treatment compliance

6.4.1 Drug treatment compliance

Throughout the trial, the investigator will remind the patients to follow the trial procedures and requirements to encourage patient compliance.

When patients are dosed at the site in the main trial and in the PK sub-study ([Table 1-1](#) and [Table 1-2](#), respectively), they will receive trial product directly from the investigator or designee, under medical supervision. The date and time of each dose administered at the site will be recorded in the source documents. Site staff will observe ingestion of the tablet. If in doubt whether the tablet has been swallowed, site staff will enter into a dialogue with the patients, acknowledging non-compliance can happen and addressing barriers to compliance.

When patients self-administer trial product at home, compliance with trial product administration will be assessed and the assessment documented in source documents at each visit where information is available.

Treatment compliance will be assessed by monitoring of drug accountability and by discussing treatment compliance and dosing conditions with the patient. Treatment compliance is defined as taking between 80-120% of the dose as prescribed between visits. The investigator must assess the amount of trial products returned compared to what was dispensed at the previous visit.

If any suspicion of non-compliance arises, apart from occasional missed doses, the site must enter into a dialogue with the patient, re-emphasising the importance of compliance and uncovering barriers to compliance. This dialogue must be documented. Compliance will be assessed by cross checking the following sources and comparing these to the expected use:

- Drug accountability information; counting returned tablets
- Questioning of patients: Discussing treatment compliance and dosing conditions with the patient

Treatment start and stop dates will be recorded in the eCRF.

6.5 Concomitant medication

During the treatment period, all oral background medication must first be ingested 30 minutes after oral trial product has been taken in the morning.

Lipid-lowering therapies

Patients must be on maximally tolerated dose of statins for at least 30 days before screening or have documented evidence of intolerance to all doses of at least 2 different statins (see Appendix 7 (Section [10.7](#))).

Other lipid lowering therapies are allowed as background therapy (except PCSK9i therapy, see below section on Prohibited concomitant medication) if patients are on a stable dose for ≥ 30 days before screening (see Section [5.1](#)).

Patients must continue their background medication (maximally tolerated dose of statins and other lipid-lowering therapies) throughout the entire trial. The background medication must be maintained at the same dose level as given at screening (visit 1) and with the same frequency during the entire treatment period unless any safety concerns related to the background medication arise. .

Prohibited concomitant medication

The following medications must not be used prior to the screening visit and during the trial:

- PCSK9i therapy: Alirocumab or evolocumab 90 days prior to screening
- PCSK9 siRNA therapy: Inclisiran 12 months prior to screening
- Oral semaglutide therapy within 30 days prior to screening

Recording the use of concomitant medication

Any medication or vaccine (including over-the-counter and prescription medicines) other than the trial product that the patient is receiving at the time of the first visit (screening visit) or receives during the trial must be recorded along with:

- Trade name or generic name
- Indication
- Dates of administration including start and stop dates

For lipid-lowering and CV medication, the following should be also collected:

- Dose and unit
- Frequency
- Route of administration

Information on concomitant medication must be recorded in the concomitant medication form in eCRF.

Changes in concomitant medication must be recorded at each visit. If a change is due to an AE, then this must be reported according to Section [8.4](#).

